## 2.6 Sample size estimation

The sample size was calculated using PASS, Inequality Tests for Two Means (2-sample t-test) to test for superiority of improvement of ETDQ-7 scores at 6 weeks and was based on the following assumptions:

- Significance level (1-sided alpha) = 0.025
- Power = 80%
- Mean change in overall ETDQ-7 score in the balloon dilation group = -2.15
- Mean change in overall ETDQ-7 score in control group = -0.85
- Common standard deviation for both groups = 1.3

Under the assumptions outlined above, a total sample size of 34 randomized subjects (17 per arm) is adequate to test this hypothesis. To account for up to 10% attrition, a minimum of 40 subjects will be enrolled in Phase 2 of the study.

## 2.7 Data analyses

Summary statistics will be calculated for all study endpoints. Categorical variables will be summarized using frequency distributions and continuous variables will be summarized with means, standard deviations, and ranges. Confidence intervals (95% CI) may be computed for select study endpoint measures. The primary efficacy endpoint will be tested at a 1-sided alpha level of 0.025. The secondary endpoint of the mean change in the overall ETDQ-7 score from baseline to follow-up in subjects treated with balloon dilation will be tested at a 2-sided alpha level of 0.05.

Subjects who are randomized but drop out before receiving their randomized treatment (balloon dilation or completion of the 6-week continued medical therapy) will not be included in the data analysis.

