## 2.4 Study size and duration

Initially, up to 10 subjects will be enrolled at up to 3 US investigational centers and treated with balloon dilation (phase 1). The second phase will include enrollment of an additional 40 subjects randomized 1:1 to balloon dilation or continued current medical therapy (control) at up to 7 investigational centers. Additional subjects may be added as needed upon approval from FDA.

It is anticipated that the first 10 subjects from phase 1 will be pooled with the remaining balloon dilation subjects for the final analysis cohort based on similar inclusion/exclusion criteria and data collection.

The expected duration of the study is 17 to 24 months. It is estimated that enrollment will take from 6 to 12 months. When a minimum of 34 phase 2 subjects have completed 6 weeks of follow-up, and a minimum of 25 phase 1 and phase 2 subjects treated with balloon dilation have completed at least 6 months of follow-up, a 510(k) application will be submitted to the FDA to obtain clearance for the new indication. All treated subjects will continue follow-up through 12 months for publication purposes. Control subjects who do not crossover to the balloon dilation treatment will be exited from the study at 6 weeks after randomization.

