## 2.5 Study hypothesis

The study is designed to test the primary efficacy endpoint hypothesis that ETD symptom improvement after balloon dilation is superior to the control group.

The following hypothesis will be tested in the comparison of mean change from baseline in overall ETDQ-7 scores at 6 weeks using a 1-sided Student's t-test where a p value less than 0.025 will be considered statistically significant:

Ho:  $d \geq 0$

Ha:  $d < 0$

Where  $d$  is the difference between balloon dilation and control group (balloon dilation – control) for the mean change from baseline to 6 weeks in the overall ETDQ-7 score.

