### 2.7.2 Missing data

Missing data can impact the integrity and credibility of any clinical study. Therefore, all attempts will be made to minimize missing data. These attempts include training of the investigators and site personnel and discussions with the subjects during the informed consent process on the importance of accurate and complete data collection. The study sponsor will track issues with sites regarding missing data through the usual monitoring process. Analyses that account for missing data will be conducted on the primary efficacy endpoint for a change from baseline.

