## 2.9 Methods and procedures

Study methods and procedures are described below. An overview of the required Phase 2 study assessments at each follow-up visit is provided in **Table 1**. Each subject's follow-up schedule is based on the date of randomization (control arm) or the study procedure (balloon dilation arm and crossover subjects).

Table 1. Phase 2 Study Assessment Schedule

Study evaluation	Baseline Within 60 days of procedure for balloon dilation arm	6-Week crossover evaluation (control arm only) ± 7 days	Procedure Within 60 days of baseline or 6-week crossover evaluation	6-Week post procedure ± 7 days	3-Month post procedure ± 15 days	6-Month post procedure ± 30 days (for 510(k) and publication)	12-Month post procedure ± 45 days (for publication)
Informed consent	✓						
Eligibility assessment	✓	✓					
Demographics/history	✓						
CT scan without contrast	✓ a						
Symptoms/exam	✓	✓		✓	✓	✓	✓
Medications b	✓	✓	✓	✓	✓	✓	✓
Nasal endoscopy	✓	✓		✓	✓	✓	✓
Otoscopy examination	✓	✓		✓	✓	✓	✓
Tympanometry	✓	✓		✓	✓	✓	✓
Valsalva evaluation	✓	✓		✓	✓	✓	✓
EQ-5D questionnaire	✓	✓		✓	✓	✓	✓
ETDQ-7 questionnaire	✓	✓		✓	✓	✓	✓
Ear infection assessment	✓ c			✓	✓	✓	✓

Study evaluation	Baseline Within 60 days of procedure for balloon dilation arm	6-Week crossover evaluation (control arm only) ± 7 days	Procedure Within 60 days of baseline or 6-week crossover evaluation	6-Week post procedure ± 7 days	3-Month post procedure ± 15 days	6-Month post procedure ± 30 days (for 510(k) and publication)	12-Month post procedure ± 45 days (for publication)
Audiologic examination	✓					✓	
Pregnancy test (when applicable)	✓		✓				
Procedure pain			✓ d				
Technical success			✓				
Device malfunction			✓				
Adverse events		✓	✓	✓	✓	✓	✓
Revision dilation or additional surgery				✓	✓	✓	✓
Subject satisfaction				✓	✓	✓	✓

a The eligibility CT scan can be performed within 6 months of enrollment.  
b Only ENT-related medications will be recorded (eg, antibiotics, steroids, allergy treatment, decongestants).  
c At baseline, determine the number of ear infections in the 12-month period before enrollment.  
d The pain scale should be completed before discharge from the index procedure. Subjects treated under general anesthesia are not required to assess procedure pain.

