#### 2.9.6 Balloon dilation arm assignment and procedure

Subjects should undergo the balloon dilation procedure within 60 days of the baseline assessment (randomized to balloon dilation) or the 6-week crossover evaluation (crossover subjects). All female subjects of childbearing potential are required to have a negative blood or urine pregnancy test **within 10 days before a balloon dilation procedure**.

Refer to the XprESS Instructions for Use (IFU) for specific instructions on system preparation, subject preparation, device set-up, shaping the device, and detailed treatment procedure for using XprESS to perform Eustachian tube dilation.

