#### 2.9.7 Follow-up visits

Subjects randomized to the control arm are scheduled for a follow-up visit at 6 weeks ( $\pm 7$  days) after their randomization. At this visit, control subjects will be evaluated and if their ETD symptoms persist (defined as overall ETDQ-7 score  $\geq 3$  or change  $< 0.4$ ), the subjects are eligible for crossover to balloon dilation treatment. Subjects who do not have persistent ETD symptoms are exited from the study after completion of this visit.

Subjects randomized to balloon dilation and crossover subjects are scheduled for the following postprocedure follow-up visits (window):

- 6-Week ( $\pm 7$  days)
- 3-Month ( $\pm 15$  days)
- 6-Month ( $\pm 30$  days)
- 12-Month ( $\pm 45$  days)

The following assessments are required at all follow-up visits:

- Symptom assessment
- Nasal endoscopy examination
- Otoscopy examination

- Tympanogram
- Valsalva evaluation
- Medication use since last study visit
- Ear infections since last study visit
- Revision dilation or additional surgery
- Subject satisfaction
- EQ-5D
- ETDQ-7
- Adverse events

In addition to the assessments noted above, an **audiologic examination is required at the 6-month visit.**

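### The Section 2.7 exclusion of early dropouts leaves the missing-data analyses of Section 2.7.2 unable to cover controls who leave before 6 weeks or dilation subjects who leave before the procedure

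*Combined protocol and SAP*

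**What the plan says.** The primary efficacy test (Section 2.5) is a "comparison of mean change from baseline in overall ETDQ-7 scores at 6 weeks using a 1-sided" Student's t-test between the randomized arms of Phase 2. Section 2.7 then removes randomized subjects who "drop out before receiving their randomized treatment (balloon dilation or completion of the 6-week continued medical therapy) will not be included" in the data analysis. It does not limit this to one named analysis.

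Section 2.7.2 promises: "Analyses that account for missing data will be conducted on the primary efficacy endpoint for a change from baseline". It gives no method and no population, and it does not mention the exclusion. The document defines no intention-to-treat, all-randomized or per-protocol set.

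The timing provisions decide whom the rule reaches:

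- Dilation arm, Section 2.9.6: "Subjects should undergo the balloon dilation procedure within 60 days of the baseline assessment".
- Control arm, Section 2.9.7: "Subjects randomized to the control arm are scheduled for a follow-up visit at 6 weeks" (± 7 days) after randomization.
- Section 2.9: each subject's "follow-up schedule is based on the date of randomization (control arm) or the study procedure" (dilation and crossover subjects).

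On expected losses, Section 2.6 says "To account for up to 10% attrition, a minimum of 40 subjects will be enrolled in Phase 2 of the study". Section 2.4 sets part of the submission trigger: "When a minimum of 34 phase 2 subjects have completed 6 weeks of follow-up".

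**The concern.** The exclusion depends on what happens after randomization, and receipt of treatment means different things in the two arms. A dilation subject counts as treated on the day of the procedure and stays in the set even if lost the next day. A control counts as treated only on completing 6 weeks, which is also when the endpoint is measured. Every control who drops out before that point is therefore removed, while a dilation subject lost between procedure and 6-week visit is kept.

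This is the trial's only randomized efficacy comparison. If subjects who leave differ from those who stay, the observed difference is biased, and the analyses promised in Section 2.7.2 are the only planned look at how much that could matter. A check that can vary the outcomes of some lost dilation subjects, but of no early control dropouts, examines only part of the problem. Section 2.9.5 offers crossover only after 6 weeks and only if symptoms persist. That could make improved controls less inclined to stay, but nothing in the documents shows who would leave.

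**Working it through.** **Inputs.** From Section 2.6: mean changes −2.15 and −0.85 (difference 1.30 in size), SD 1.3, one-sided alpha 0.025, 80% power, 34 evaluable subjects, up to 10% attrition, 40 enrolled. From Section 2.1: 1:1 allocation, taken as 20 per arm. Assumed, because the documents do not give them: how losses divide between arms, when they occur, and how leavers differ.

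**1. The plan's own figure.** For a two-sample t-test, the noncentrality at 17 per arm is 1.30 / (1.3 × √(2/17)) = 2.915 on 32 degrees of freedom, giving 80.7% power. With 16 per arm it is 78.1%. So 34 reproduces. Allowing for attrition, 34 / 0.90 = 37.8, or 38, and 40 covers this. Ten percent of 40 is 4 losses; falling to 34 takes 6 losses, or 15%.

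**2. Who is covered.** Phase 2 subjects with no 6-week score, under the literal wording:

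| Subject | Kept by Section 2.7? | Within reach of Section 2.7.2? |
|---|---|---|
| Dilation, drops out before procedure | No | No |
| Dilation, dilated, lost before 6-week visit | Yes | Yes |
| Dilation, stays in study but never dilated | Yes (not a dropout) | Yes, but no method is given, and without a procedure there is no date for the visit |
| Control, drops out before completing 6 weeks | No | No |
| Control, completes 6 weeks but lacks a score | Yes | Yes |

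**3. Effect on the primary t-test.** The two excluded groups have no 6-week score, so the t-test on observed scores would omit them with or without the rule. The loss falls on the missing-data analyses.

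**4. Illustration of what those analyses can probe.** Suppose lost subjects' outcomes are shifted by 1.3 points (1 SD), in opposite directions in the two arms, and every control loss is a dropout before 6 weeks. The movement in the between-arm difference is:

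- all randomized: (dilation losses + control losses) / 20 × 1.3
- under the rule: post-procedure dilation losses / (20 − pre-procedure losses) × 1.3

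| 4 losses | All randomized | Under the rule |
|---|---|---|
| 2 post-procedure, 2 control | 4/20 × 1.3 = 0.26 | 2/20 × 1.3 = 0.13 |
| 2 pre-procedure, 2 control | 0.26 | 0/18 × 1.3 = 0 |
| 4 post-procedure | 0.26 | 4/20 × 1.3 = 0.26 |

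The rule removes half of the reach in the first case, all of it in the second and none in the third.

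**The case against.** The strongest reply is that Section 2.7.2 comes later and is the more specific provision. The sponsor may have meant its analyses to bring early dropouts back. That is possible, but the text does not say so, and Section 2.7 speaks of the data analysis without qualification. An ambiguity about who is analyzed should be settled before data are seen. A second reply, that the primary t-test is almost unaffected, is correct and limits the point. A third is that the 1.3-point shift is arbitrary. It is, since a tipping-point analysis would vary it; the table shows only which losses can be examined at all.

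Several stronger readings are tempting and are not supported:

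- A reader might infer that the missing-data analyses cannot test the randomized comparison at all. They are not empty: two groups in the table above remain fully in reach.
- A reader might compute type I error for selective dropout and blame the rule. Such bias belongs to the observed-score t-test, would arise without the rule, and is not removed by the fix below.
- A reader might infer that the bias favors the device. The documents give no dropout by arm and no outcomes for leavers.
- A reader might take the control exclusion to run from 35 to 49 days. The ± 7 days is a visit window; the rule refers to completing 6 weeks of therapy.

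Nor can the matter be dismissed because a result at the planned effect would survive any plausible shift. With 3 losses per arm, the same assumptions give 6/20 × 1.3 = 0.39 and 1.30 − 0.39 = 0.91. The critical difference at 17 observed per arm is 0.908, which leaves practically no margin. With 2 losses per arm, 1.30 − 0.26 = 1.04 is above the 0.881 that applies at 18 per arm.

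**Conclusion.** The concern holds as a limit on the planned sensitivity check. Read literally, Sections 2.7 and 2.7.2 together leave out all controls who drop out before 6 weeks and all dilation subjects who drop out before the procedure, while keeping dilated subjects lost later. The exclusion acts after randomization and works differently by arm, so the check on the only randomized efficacy test is incomplete.

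The extent depends on assumptions that the documents cannot settle. For 4 losses and a 1.3-point shift, the check reaches between 0 and 0.26 points, against 0.26 on all randomized subjects, with no harm if every loss follows the procedure. The size and direction of any actual bias are unknown. The sample size and the primary test are not shown to be wrong. This is an inexpensive improvement to the plan.

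**What to change.** Replace the exclusion sentence in Section 2.7 with:

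> The primary efficacy analysis set is all randomized Phase 2 subjects, analyzed in the arm to which they were randomized, including any subject with a 6-week ETDQ-7 score whether or not the assigned treatment was received or completed.

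Keep the t-test on observed scores as the primary test. In Section 2.7.2 state that:

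1. The missing-data analyses are run on all randomized Phase 2 subjects.
2. Missing 6-week scores are multiply imputed using baseline ETDQ-7.
3. A dilation-arm subject with no 6-week score who was never dilated, whether withdrawn or still in the study, is not imputed from dilated completers. Imputing from the control arm is one option.
4. Scores after crossover are not used.
5. A tipping-point analysis varies the assumed outcome separately in each arm.

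Keep the present exclusion rule as a supportive analysis.

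The cost is wording, one imputation analysis and one tipping-point analysis, with no added visit or subject. Power of the primary t-test on observed scores is unchanged (83.0% at 18 per arm). The drawback is a diluted sensitivity estimate with less power. If 2 dilation subjects leave undilated and 2 controls leave, and all four are given the control mean, the dilation mean change becomes (18 × −2.15 + 2 × −0.85) / 20 = −2.02 and the difference 2.02 − 0.85 = 1.17. Power is then about 77% if imputed values are treated as observed; a simulation with multiple imputation gave about 75%.

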### 2.7.1 Poolability analysis

Poolability of the primary efficacy endpoint between investigational centers will be evaluated. This assessment will evaluate the significance of any differences or imbalances that exist across investigational centers in the primary endpoint. Centers with less than 5 patients enrolled will be combined into a pseudocenter for purposes of analysis. To protect against having an overly large pseudocenter, when one pseudocenter exceeds 5 subjects, a second pseudocenter will be formed. This process will continue as needed each time a pseudocenter exceeds 5 subjects.

The type III p value from an ANOVA model will be used to assess center poolability for the primary efficacy endpoint. An alpha level of 0.15 will be used to assess statistical significance of the center effect.

### 2.7.2 Missing data

Missing data can impact the integrity and credibility of any clinical study. Therefore, all attempts will be made to minimize missing data. These attempts include training of the investigators and site personnel and discussions with the subjects during the informed consent process on the importance of accurate and complete data collection. The study sponsor will track issues with sites regarding missing data through the usual monitoring process. Analyses that account for missing data will be conducted on the primary efficacy endpoint for a change from baseline.

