## 1.2 Purpose

The purpose of the current study is to collect 6-month safety and efficacy data on the use of the XprESS device to support a 510(k) application to FDA to add a new indication for use. Six- and 12-month data will also be collected for publication purposes.

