## 2.3 Study endpoints

### 2.3.1 Primary endpoints

The following measures will be collected as the primary endpoints:

- Comparison of mean change in overall ETDQ-7 score from baseline to 6 weeks between balloon dilation arm and control arm
- Complication rate

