### 2.3.2 Secondary endpoints

The following measures will be collected as secondary endpoints:

- Mean change in overall ETDQ-7 score from baseline to follow-up (balloon dilation subjects)
- Technical success rate
- Revision dilation rate

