#### 2.10.1 Primary and secondary endpoint assessments

##### *Mean change in overall ETDQ-7 score*

The Eustachian Tube Dysfunction Questionnaire (ETDQ-7) is a standardized, 7-item questionnaire designed to assess quality of life associated with Eustachian tube dysfunction. The 7 dimensions of the questionnaire are pressure, pain, feeling clogged, cold/sinusitis problems, crackling/popping, ringing, and feeling muffled. Each item is assessed on a 1 (no problem) to 7 (severe problem) scale and an overall score, which is the mean of the 7 dimension scores, is calculated. The questionnaire is designed to be self-completed by the subject. ETDQ-7 questionnaires will be completed at baseline and at all study visits. Changes in overall ETDQ-7 scores will be based on the mean change between the baseline assessment (or 6-week crossover

evaluation for crossover subjects) and each follow-up assessment. Standard treatment effect size may also be calculated for the mean overall ETDQ-7 score. The ETDQ-7 CRF may be considered a source document if completed directly by the subject on the CRF.

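### No missing-data method is set for the ETDQ-7 change in dilated subjects at 6 and 12 months; a mean of those seen would overstate the size of benefit if poorer responders are absent more often

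*Combined protocol and SAP*

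**What the plan says.** Section 2.7.2 describes steps to prevent missing data and then makes one analytic commitment: "Analyses that account for missing data will be conducted on the primary efficacy endpoint for a change from baseline". It names no method. Section 2.3.1 defines the primary efficacy endpoint as "Comparison of mean change in overall ETDQ-7 score from baseline to 6 weeks between balloon dilation arm and control arm", so the commitment stops at 6 weeks.

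Section 2.7 gives a formal test, 2-sided at 0.05, to another ETDQ-7 endpoint: "The secondary endpoint of the mean change in the overall ETDQ-7 score from baseline to follow-up in subjects treated with balloon dilation". Neither section 2.3.2 nor section 2.7 names its time point or estimator. Section 2.10.1 adds "Changes in overall ETDQ-7 scores will be based on the mean change between the baseline assessment" (the 6-week crossover evaluation, for crossover subjects) and each later assessment. It gives no rule for absent scores. The exclusion in section 2.7 covers only subjects who drop out before receiving their randomized treatment, so it does not reach a treated subject who misses month 6.

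Section 1.2 states the study's purpose as to "collect 6-month safety and efficacy data on the use of the XprESS device" in support of a 510(k). Section 2.4 allows submission once at least 34 Phase 2 subjects have completed 6 weeks and "a minimum of 25 phase 1 and phase 2 subjects treated with balloon dilation have completed at least 6 months of follow-up".

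**The concern.** Missing-data analysis is promised for the earliest postprocedure visit and not for the later visits, where more subjects are likely to be absent. Controls exit or become eligible to cross over at 6 weeks, so the 6-month ETDQ-7 evidence has a single arm, and no comparator shares the attrition and offsets part of its effect.

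With no rule stated, the natural estimate at each visit is the mean of those who attended. If absence is related to poor early response, the 6-month mean improves because those subjects are gone. Their 6-week and 3-month scores, which carry information about the missing value, would not enter the 6-month estimate. What is at stake is the size of the 6- and 12-month benefit that is reported.

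**Working it through.** **Inputs from the plan (section 2.6).** Mean change -2.15 (dilation) and -0.85 (control), SD 1.3, 1-sided alpha 0.025, power 80%, attrition up to 10%. These serve the 6-week comparison. No attrition figure is given for 6 or 12 months.

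**Reproducing the plan's figure.** The difference is 1.30 with SD 1.3. The exact two-sample t-test has power 78.1% at 16 per arm and 80.7% at 17, so 34 in total is confirmed. Allowing for 10% loss, 34/0.9 = 37.8, or 38; the plan enrols 40. The point below does not change the sample size.

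**Size if loss follows the 6-week score.** Assumptions: the true mean change is -2.15 with SD 1.3 at both 6 weeks and 6 months; the between-visit correlation r is 0.4 to 0.8; the log-odds of loss rise by b = 0.5 to 1.0 per point of poorer 6-week change; the loss m is 10% to 30%. Let k be the amount, in SD units, by which the mean 6-week change of those still seen is better than that of all treated subjects. It is found by integrating the normal distribution against the logistic loss. Then

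overstatement at 6 months = r × 1.3 × k.

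| Loss m | k (b = 0.5) | k (b = 1.0) | Smallest (r = 0.4, b = 0.5) | Largest (r = 0.8, b = 1.0) |
|---|---|---|---|---|
| 10% | 0.062 | 0.111 | 0.03 | 0.12 |
| 20% | 0.122 | 0.208 | 0.06 | 0.22 |
| 30% | 0.180 | 0.301 | 0.09 | 0.31 |

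At r = 0.6 and 20% loss, the mean of those seen is -2.24 to -2.31 against a true -2.15. A likelihood estimate that uses the 6-week score returns -2.15 here, but only because loss was made to depend on that observed score.

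**If loss depends on the unseen 6-month score** (r = 0.6, 20% loss, same slopes), the mean of those seen is -2.31 to -2.42 and the likelihood estimate is -2.25 to -2.33. About a third of the bias is removed.

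**Direct bound.** Suppose subjects seen improve by -2.15 and those lost have mean change D. The overstatement is then m × (D + 2.15).
- m = 10%: 0.13 for D = -0.85, and 0.22 for D = 0.
- m = 16.7% (25 of 30 seen): 0.22 for D = -0.85, and 0.36 for D = 0.

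**Effect on the test.** Set every missing score to zero change. The variance is (1 - m) × 1.3² + m(1 - m) × 2.15².
- 25 of 30 seen: mean -1.79, SD 1.43, t = -1.79/(1.43/√30) = -6.9.
- 25 of 50 seen: mean -1.08, SD 1.41, t = -5.4.

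**Where 30 and 50 come from.** Phase 1 treats 10 and the Phase 2 dilation arm 20, giving 30. If all 20 controls cross over, the total is 50.

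**The case against.** The strongest reply is that the plan is silent and does not prescribe a faulty method. A reader might infer that the plan adopts a complete-case mean and discards earlier scores. Neither is written. Section 2.10.1 uses the 6-week and 3-month scores for their own visits and says nothing about absent ones. An observed-case mean is the likely default, and the point stands only in that form.

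Selective loss is also an assumption. Section 2.9.8 permits revision, other surgery and medical treatment for subjects without relief, and treated subjects are followed to 12 months, which gives them a reason to stay. This weakens the dropout argument, but it exposes another gap: the plan does not say how scores after such procedures are analysed, and a mixed model would absorb them without comment.

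A reader might take 25 seen out of 50 treated as evidence of heavy dropout. It is not. Twenty-five is a minimum that triggers submission, 50 requires every control to cross over, and subjects not yet due at 6 months are absent for administrative reasons. That is no reason to expect poor responders among them.

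Finally, the effect is modest. At the plan's only attrition figure, 10%, the dropout model gives 0.03 to 0.12 points. The 95% confidence interval half-width at n = 25 is 2.064 × 1.3/5 = 0.54, and the plan's own threshold for persisting symptoms is a change below 0.4. This argues against a severe rating. It does not remove the gap, because a wide interval does not correct a bias in one direction and the remedy uses data already collected.

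**Conclusion.** The concern holds in limited form. Missing-data analyses are confined to the 6-week primary endpoint, while the tested secondary change, which carries the 6-month efficacy evidence, has none.

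If subjects with a poorer early response are absent more often, a mean of those seen overstates the size of benefit by roughly 0.03 to 0.12 points at 10% loss and up to about 0.31 at 30%. The direct bound, which fixes the mean of those lost at the control value or at zero, gives 0.13 to 0.22 at 10%. All of these rest on assumed dropout patterns and on carrying the plan's 6-week mean and SD forward to 6 months.

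A reader might infer that the significance of the secondary test is in doubt. The figures do not support that: with all missing scores set to zero change, t is still -6.9 (25 of 30 seen) or -5.4 (25 of 50). This is an inexpensive improvement that should be made. It does not invalidate the study.

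**What to change.** **In section 2.7**, estimate the secondary change with a mixed model for repeated measures over all postprocedure ETDQ-7 scores of dilated subjects (6 weeks, 3, 6 and 12 months). Use visit as a factor and an unstructured covariance, with a simpler structure named in advance in case it does not converge at this sample size. Name the 6-month estimate as the reported one.

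**In section 2.7.2:**
- Extend the missing-data analyses to this endpoint, with one conservative sensitivity analysis: either set missing scores of subjects who left to zero change, or run a tipping-point analysis. Giving them the control mean of -0.85 would be too lenient. It is more than twice the 0.4 threshold, and in the dropout model above 27% to 51% of those lost already have a 6-week change worse than that.
- Treat subjects not yet due at 6 months separately from dropouts.
- Report the number seen out of the number treated at each visit.
- State how scores after revision dilation or other surgery are analysed.

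**Cost.** Wording and minor programming, with no new data, visits or subjects. The 6-month estimate may be slightly less favourable. The model corrects loss explained by observed scores and only part of loss that depends on unseen ones, which is why the sensitivity analysis is needed.
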